11.3.5 Implant

Implant refers to a subject who is successfully implanted with the ImageReady System per the study protocol. These subjects are followed in accordance with the follow-up schedule and included in all analyses of safety and performance.

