13.1.1 Primary Safety Endpoint: MR Scan-Related ImageReady System Complication Free Rate

The primary safety endpoint will be assessed for all subjects who undergo any portion of the study-required MR scan sequences. Safety will be confirmed by evaluating the **MR scan-related ImageReady System** Complication-free rate (CFR) between the MR Scan and the MRI Visit + 1 Month. For the purpose of this endpoint, a MR scan-related ImageReady System complication will be defined as those complications that are related to the MR scan and ImageReady System. All complications that the site reports as related to the MR scan and ImageReady System will be adjudicated by an external committee for relation to the MR scan. Complications that are determined to be associated with the MR scan will be considered MR scan-related complications and count against this endpoint.

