13.1.1.3 Statistical Methods

Endpoint analysis will be performed on all subjects that undergo an MR scan (study sequence is initiated), including subjects that have an incomplete scan. However, if a medically necessary scan occurs between implant and the MRI + 1 Month Visit, data for that subject will not be included in this endpoint.

[REDACTED]

The Kaplan-Meier methodology was chosen for this endpoint to utilize all available data for each subject. Subjects, who did not undergo an MR scan, i.e., the study sequence was not initiated, will be considered to have missing data. To assess the robustness of this analysis method and the potential impact missing data could have had on the analysis results, a tipping point analysis will be conducted that will include enrolled subjects. The tipping point analysis will assign each subject with missing data as either having or not having a MR Scan-related complication. All possible combinations of these patients' data will be evaluated along with the actual observed data to find the point, if any, at which the endpoint is failed.

13.1.2 Primary RV Effectiveness Endpoint 1: Pre-MR Scan vs. 1 Month Post-MR Scan RV Pacing Threshold at 0.5 ms

Increases in RV pacing threshold (at 0.5 ms) pre- MR scan and 1 Month post-MR scan will be calculated for subjects. Subjects that have an increase in average pacing thresholds $\leq 0.5V$ (at 0.5 ms) from pre-MR Scan to MRI Visit + 1 Month follow-up will be considered a success.

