23.1 Clinical Events Committee

A CEC is an independent group of individuals with pertinent expertise that reviews and adjudicates all of the following, as reported by study investigators for Phase I and II subjects:

- Events related to the study-required MR scan and ImageReady System between the MRI Visit and MRI + 1 month Visit (safety endpoint)
- Events related to medically necessary scan(s) and ImageReady System
- Subject deaths

The CEC will review a safety event dossier, which may include copies of subject source documents provided by study sites. At the discretion of the sponsor, additional events may be sent to the CEC.

Committee members will include a minimum of three practitioners with training in Electrophysiology (EP), and/ or Cardiology with the necessary therapeutic and subject matter expertise to adjudicate the event categories outlined above. CEC responsibilities, qualifications, membership, and committee procedures are outlined in the CEC charter.

24. Suspension or Termination

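### The primary safety rule excludes a scanned subject who has a medically necessary scan before the 1-month visit, with no readable exception for an adjudicated study-scan complication that came first

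*Combined protocol and SAP*

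**What the plan says.** Section 13.1.1 defines the safety population broadly: "The primary safety endpoint will be assessed for all subjects who undergo any portion of the study-required MR scan sequences". On events it says: "Complications that are determined to be associated with the MR scan will be considered MR scan-related complications and count against this endpoint".

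Section 13.1.1.3 starts from the same population, namely every subject whose study sequence was initiated, incomplete scans included. It then adds an exception: "if a medically necessary scan occurs between implant and the MRI + 1 Month Visit, data for that subject will not be included" in this endpoint. The exception does not depend on whether the medically necessary scan came before or after the study scan, or on whether a complication had already occurred. A redacted block follows.

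After that block the section explains the method: "The Kaplan-Meier methodology was chosen for this endpoint to utilize all available data for each subject". It then defines missing data for the tipping-point analysis: "Subjects, who did not undergo an MR scan, i.e., the study sequence was not initiated, will be considered to have missing data".

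For the four effectiveness endpoints (13.1.2.3, 13.1.3.3, 13.1.4.3 and 13.1.5.3), a medically necessary scan in the same window also leads to exclusion. Those sections, however, treat the excluded subjects as missing in the tipping-point analysis.

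Section 23.1 has the Clinical Events Committee adjudicate study-scan events and medically-necessary-scan events ("Events related to medically necessary scan(s) and ImageReady System") as separate categories.

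**The concern.** Take a subject who has the study scan, then an adjudicated study-scan complication, and then an unforeseen medically necessary scan before the MRI + 1 Month Visit. The rule as worded takes that subject, with the event, out of the primary safety estimate and test. The documents do not describe this case; it follows from an unqualified sentence.

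Two things make this more than untidy wording. First, when the medically necessary scan comes after the study scan, inclusion depends on something that happened after exposure. If a complication or its work-up makes such a scan more likely, exclusion favours the device. The documents give no data on whether it does. Second, the Kaplan-Meier method could use follow-up until the later scan and stop there, so whole-subject exclusion discards information that the method was chosen to keep.

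At stake are a small shift in the safety estimate, a possible change of result near the pass limit, and a safety analysis set that differs between 13.1.1 and 13.1.1.3.

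**Working it through.** **No plan figure to reproduce.** The safety sample size, expected rate and power are redacted. The calculation illustrates sensitivity only.

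**Inputs**
- Performance goal: complication-free rate above 90% (13.1.1.1), so a 10% complication rate under the null.
- Significance level: 2.5% (13.4.2). One-sided is an assumption, made because the alternative is directional.
- Scanned subjects N: 150, 200 and 300, all assumed.
- Test: exact binomial as a stand-in for Kaplan-Meier, with no censoring.

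**Formula.** p = P(X ≤ e), where X ~ Binomial(n, 0.10) and e is the number of subjects with an event. The goal is met if p ≤ 0.025. The pass limit k is the largest e that meets it.

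**Excluding one subject with an event, starting one above the limit**

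| N | k | All kept | One event subject excluded |
|---|---|---|---|
| 150 | 7 | 8/150, p=0.031, not met | 7/149, p=0.015, met |
| 200 | 11 | 12/200, p=0.032, not met | 11/199, p=0.018, met |
| 300 | 19 | 20/300, p=0.029, not met | 19/299, p=0.018, met |

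**Excluding one event-free subject, starting at the limit.** The effect is small and runs against the device: 11/200 (p=0.0168) becomes 11/199 (p=0.0177) and still passes. A pass can be lost at some N: 4/100 (p=0.0237) becomes 4/99 (p=0.0254).

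**Away from the limit.** 5/200 is 97.50% complication-free. Excluding one event subject gives 4/199 = 97.99%; excluding one event-free subject gives 5/199 = 97.49%. All pass.

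**How likely is a reversal?** One exclusion can turn a fail into a pass only if exactly k+1 events occur. At N=200 that is P(X=12) under Binomial(200, r), where r is the true complication rate. At least one of the 12 must also have a qualifying scan. If each has that chance q independently, the joint probability is P(X=12) × [1 − (1−q)^12]. With q = 1% (assumed), the bracket is 1 − 0.99^12 = 0.114.

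| True rate r | P(X=12) | Joint, q=1% |
|---|---|---|
| 2% | 0.0006 | 0.00006 |
| 3% | 0.011 | 0.0012 |
| 5% | 0.097 | 0.011 |

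At r=3%, moving q from 0.5% to 5% moves the joint probability from 0.0006 to 0.005. If scans are more likely after an event, q is higher.

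**Timing under the Conditions of Use.** Section 6.1 requires at least six weeks (42 days) after any lead revision or surgical modification, and no evidence of compromised system integrity. The MRI + 1 Month Visit is due by day 30 + 7 = 37. A surgical revision after the study scan therefore leaves no room for an on-label scan before a visit held on time. What mainly remains is complications corrected without system surgery (Table 21-2 counts intravenous medication as invasive correction), off-label scans and late visits.

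**The case against.** The strongest reply is that this is an open, prespecified exception, applied to all five primary endpoints, that keeps a second MR exposure out of the estimate. That is a fair aim, and it justifies excluding a subject whose medically necessary scan preceded the study scan. It does not justify dropping an event that occurred before the later scan, where the second exposure cannot have contributed.

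A reader might infer a flat contradiction with Section 11.3.5, which says that implanted subjects are "included in all analyses of safety and performance", and with Section 23.1, which lists "Events related to the study-required MR scan and ImageReady System between the MRI Visit and MRI + 1 month Visit (safety endpoint") without exception. The documents do not support that reading. The first is subject-classification text and the second sets the committee's scope; an explicit exception in a methods section can narrow both. The tension that stands is with 13.1.1 and with the stated reason for Kaplan-Meier.

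The safety tipping-point text also says that the analysis will take in enrolled subjects, which could be stretched to scanned subjects excluded under this rule. The missing-data definition beside it is narrower, so the coverage is unclear rather than plainly absent.

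Rarity stands as an objection to size. Exclusion criterion 4 and the Conditions of Use leave few routes to the case. The redaction also stands: event or censoring rules could sit in the block directly after the sentence.

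Finally, the events are not lost. Section 21.1 requires MRI-scan-related adverse events to be reported, the committee adjudicates those reported as related to the scan and the system, and 13.2.5 summarises complications of medically necessary scans. None of that restores a study-scan event to the primary estimate.

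**Conclusion.** The point holds with moderate confidence. On the readable text, a scanned subject leaves the primary safety endpoint because of a medically necessary scan in the window, even if an adjudicated study-scan complication came first, and the tipping-point analysis does not clearly recover that subject.

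The effect is small. One excluded event moves the estimate by about half a percentage point at 5/200 and changes the result only at one event above the limit. A reversal is unlikely unless the true complication rate is about 3% or more. This rests on assumed N, a binomial proxy, a one-sided 2.5% test and an assumed chance of a later scan.

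Two stronger readings might be inferred. One is that the safety conclusion is unreliable; the probabilities above do not support that, and the documents give no count of affected subjects. The other is that the whole exclusion should go; that would bring subjects scanned before the study scan, and follow-up after a second exposure, into the primary analysis. The defect is narrower: the rule ignores the order of events.

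**What to change.** Replace the sentence in 13.1.1.3 with a rule that depends on order:

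- **Medically necessary scan after the study scan:** keep the subject, count every committee-adjudicated study-scan complication with onset before that scan, and censor event-free subjects at that scan.
- **Medically necessary scan before the study scan:** keep the exclusion.
- **Anyone still excluded:** add to the tipping-point set, as the effectiveness analyses do.
- **Sensitivity analysis:** also count complications that the committee attributes to the study scan but that begin after the later scan.
- **Listing:** show each affected subject, the order of the two scans and the reason for the medically necessary one.

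If the redacted block already states such a rule, align the sentence with it.

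The cost is protocol and SAP wording, with no new data. The safety estimate may be slightly less favourable, and a few subjects would be censored early. Attribution after a second scan is less certain, so later events belong in the sensitivity analysis rather than the primary one.

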11.2 Withdrawal

All subjects enrolled in the clinical study (including those withdrawn from the clinical study or lost to follow-up) shall be accounted for and documented. If a subject withdraws from the clinical investigation, the reason(s) shall be reported.

For US subjects: If such withdrawal is due to problems related to investigational device safety or performance, the investigator shall ask for the subject’s permission to follow his/her status/condition outside of the clinical study until the implanted investigational devices are approved by the FDA or the device is explanted.

Reasons for withdrawal include, but are not limited to:

- Subject who does not receive a Boston Scientific ImageReady MR Conditional Defibrillation System (no follow-up requirements)
- Subject who receive only a partial Boston Scientific ImageReady MR Conditional Defibrillation System (see section 11.3.4 for follow-up requirements)
- Subjects that have a PG or lead changeout that is not a Boston Scientific ImageReady MR Conditional Defibrillation System component (See Section 5)
- Subjects in Phase I who refuse to undergo the study require MR scan and are not willing to be rolled into Phase II
- Subjects already enrolled with previous protocol versions, who have not performed the MRI visit and who meet the updated exclusion criterion #5
- Subjects who fail the heart rhythm monitoring requirements at the MRI visit
- Physician discretion
- Subject choice to withdraw consent
- Lost to follow-up
- Death

While study withdrawal is discouraged, subjects may withdraw from the ENABLE MRI study and/or the VF Induction Sub-study at any time, with or without reason, and without prejudice to further treatment.

All applicable case report forms up to the point of subject withdrawal and a “Subject Status” form must be completed. Subjects who are “lost-to-follow-up” should have documented attempts to contact them prior to completion of the “Subject Status” form.

Additional study data may no longer be collected after the point at which a subject has been withdrawn from the study or withdraws his/her consent, for whatever reason. All open adverse events should be closed or documented as chronic. Data collected up to the point of subject withdrawal may be used.

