11.3.1 Intent

Intent refers to a subject who has been enrolled, but does not have the lead(s) or PG introduced into their body. There are no follow-up requirements for intent subjects. The

original informed consent form (ICF) and screening documentation for intent subjects should be maintained in the Center's files.

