11.3.4 Partial Implant

Partial Implant refers to a subject who is implanted with a component of the ImageReady System during the implant procedure, but does not end up with a complete ImageReady System. Due to the fact that these subjects do not have a full ImageReady System, according to the Conditions of Use in the *BSC MRI Technical Guide*, they shall not receive the MR Scan for the ENABLE MRI study.

- **For US subjects: If investigational leads were implanted, the subjects must be followed for safety.** These subjects must be followed at each time point required for the study until the implanted investigational leads are approved by the FDA or the device is explanted.
- **If there were no investigational leads implanted,** Partial Implant subjects must be followed 30 ± 7 days post- ImageReady System implant to assure there are no associated adverse events, or to assure the resolution of any adverse events associated with the ImageReady System implant, then withdrawn from the study.

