12.7 MRI Visit (Phase I only)

The MRI follow-up visit consists of data collection and MR scan.

For Phase I de novo subjects, the visit will occur 6 to 9 weeks (42-63 days) after implant or surgical revision of the ImageReady System implant*.

For Phase I existing implant subjects, the visit will occur **within 6 weeks** (42 days) from enrollment AND at least 6 weeks after implant or surgical intervention* of the ImageReady System. For example:

- If the subject was enrolled with an ImageReady System that was implanted >6 weeks before enrollment, the MRI visit must occur within 6 weeks (42 days).
- If the subject was enrolled with the an ImageReady System that was implanted 2 weeks (14 days) before enrollment, the MRI visit must occur between 4 – 6 weeks (28 to 42 days) after enrollment.

***Note:** If a subject has had a surgical revision to their ImageReady System (i.e., a lead revision/ reposition), and the MRI Visit is unable to be scheduled within the time window, the MRI Visit and the MRI + 1 Month Visit are not required. Enter the reason for MRI Visit and MRI + 1 Month visit not being done into EDC.

Note: For subjects enrolled under prior protocol versions and who have not been through their MRI visit, the MRI visit will occur within 6 weeks (42 days) from re-consenting and after reconfirmation that they do not meet the exclusion criterion #5

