12.7.2.3 Heart Rhythm Monitoring prior to MRI protection mode programming

It is **required** that the heart rhythm be monitored by the site Principal Investigator or a sub-investigator for all subjects prior to initiation of the MRI Protection Mode and the MR Scan.

- Monitoring is to be performed in VVI 40 programming
- Monitor the heart rhythm using the programmer EGRAMs for at least 5 minutes. Heart rate and any abnormal rhythms, including incidence of ectopy shall be documented.
 - In particular, look for signs of progressive AV nodal block over time, permanent or intermittent complete AV block, or trifascicular block (alternating bundle branch block or PR > 200 ms with LBBB or other bifascicular block) or a paced event (one single paced beat) during this time period. **Any** occurrence of these events will disqualify subjects from undergoing the MRI.
 - Such subjects should be withdrawn from the study.
 - Required ECG documentation
 - 12 lead ECG and a 10s rhythm strip to be printed at any time during the 5 minutes of the monitoring (either from the ECG machine or the BSC PRM)
 - Any abnormal rhythms / ectopy shall be documented with a printed ECG or rhythm strip if possible.

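### The RV and LV sensed-amplitude tipping-point analyses impute outcomes for subjects whom the endpoint excludes at baseline (pre-scan average below 5 mV)

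*Combined protocol and SAP*

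**What the plan says.** **Sensed amplitude.** Sections 13.1.3 (RV) and 13.1.5 (LV) define success as a one-month average that is still at least 5.0 mV and more than half the pre-scan value. Both sections leave out subjects whose pre-scan average is below 5.0 mV. Sections 13.1.3.3 and 13.1.5.3 repeat this as the last of five per-protocol exclusions. The other four are a medically necessary scan, failure to meet the Conditions of Use, a lead-related complication and an incomplete scan. The paragraph after each list counts two groups as missing: subjects without paired measurements, and subjects meeting any exclusion on the list. Each is set to success or failure, over all combinations, to find where the endpoint fails.

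**Safety.** Section 13.1.1 says "The primary safety endpoint will be assessed for all subjects who undergo any portion of the study-required MR scan sequences". Section 13.1.1.3 then says "Subjects, who did not undergo an MR scan, i.e., the study sequence was not initiated, will be considered to have missing data", and that "a tipping point analysis will be conducted that will include enrolled subjects". Each such subject is assigned a scan-related complication or none. Two aims are given: robustness of the Kaplan-Meier method, and the possible effect of missing data on the results. Part of this section is redacted.

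Subjects go unscanned for different reasons. Some cannot be scanned under the plan:
- Section 11.3.1: "Intent refers to a subject who has been enrolled, but does not have the lead(s) or PG introduced into their body".
- Section 11.3.4, on partial implants: "they shall not receive the MR Scan for the ENABLE MRI study".
- Section 12.7.2.3, on rhythm findings: "occurrence of these events will disqualify subjects from undergoing the MRI".

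Others are unscanned by circumstance:
- Section 12.7, when a surgical revision makes the visit miss its window: "the MRI Visit and the MRI + 1 Month Visit are not required".
- Section 11.2, among reasons for withdrawal: "Subjects in Phase I who refuse to undergo the study require MR scan and are not willing to be rolled into Phase II".

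**The concern.** A tipping-point analysis asks how bad the unobserved outcomes of eligible subjects would have to be to overturn the result. A subject with a pre-scan average below 5 mV has no such outcome. The baseline value is known, since it is the reason for exclusion, and the success rule cannot apply to an amplitude that was never at 5 mV. Imputing a success or failure for that subject answers no question about the endpoint. It also changes both the denominator and the number of failures available to impute. The reported tipping point then depends on how many low-amplitude subjects were enrolled, and a reader would take it as a statement about missing data.

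The safety rule has a related but weaker problem. A subject whose scan never began has no time at risk for a scan-related complication. The rule also pools subjects who could not be scanned with those who merely were not, and asking what would have happened under a scan makes sense only for the second group.

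**Working it through.** **1. Sections side by side.** Below 5 mV is an exclusion in the endpoint definitions themselves (13.1.3, 13.1.5). The other four exclusions appear only in the per-protocol lists. They describe subjects who fit the endpoint definition but departed from plan or had an event, so treating those four as missing is coherent. The two pacing-threshold endpoints (13.1.2.3, 13.1.4.3) have no amplitude exclusion and are not affected.

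**2. Inputs.** From the documents: goal 85% (13.1.3.1, 13.1.5.1), significance level 5% (13.4.2), one-sided exact binomial test (synopsis statistical table). Phase I sizes, expected rates and attrition are redacted, so the plan gives no figure to reproduce. All counts below are assumed.

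**3. Formula.** Take n evaluable subjects with f failures, and add k imputed subjects of whom m are failures. The result tips at the smallest m with P(X ≥ n + k − f − m) > 0.05, where X is binomial(n + k, 0.85). This is the same as the exact one-sided 95% lower bound falling below 0.85. As written, k = (below 5 mV) + (missing). Corrected, k = missing only.

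| Case | n, f | Below 5 mV, missing | As written | Corrected |
|---|---|---|---|---|
| RV, few low | 226, 11 | 12, 12 | 17 of 24 | cannot tip |
| RV, many low | 200, 14 | 38, 12 | 14 of 50 | 9 of 12 |
| LV | 75, 4 | 20, 5 | 5 of 25 | 3 of 5 |

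Lower bounds at the tipping point:
- First case. Written: 11 + 17 = 28 failures of 250, bound 0.8497 (27 failures give 0.8541). Corrected: all 12 missing as failures gives 23 of 238, bound 0.866, still above 0.85.
- Second case. Written: 14 + 14 = 28 of 250, bound 0.8497. Corrected: 14 + 9 = 23 of 212, bound 0.8498 (22 failures give 0.8551).
- Third case. Written: 4 + 5 = 9 of 100, bound 0.8482 (8 failures give 0.8603). Corrected: 4 + 3 = 7 of 80, bound 0.8419 (6 failures give 0.8573).

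**4. Direction.** In the first case the written rule reports a tipping point where none exists. Since 17 exceeds 12, at least 5 of the imputed failures must be ineligible subjects. In the other two cases the written count is higher (14 against 9, 5 against 3), which looks more robust. As a share of those imputed it is lower (28% against 75%, 20% against 60%), which looks more fragile.

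**5. Safety, for scale only.** Goal 90% (13.1.1.1) and level 2.5% (13.4.2), taken as one-sided. An exact binomial bound stands in for Kaplan-Meier. Assume zero observed complications and 150, 200 or 250 scanned subjects. Imputing to never-scanned subjects, with an assumed 10% to 30% of enrolled subjects unscanned, the result tips at 10–13, 14–19 or 18–25 complications. Among scanned subjects alone it fails at 8, 12 or 16 in total, so incomplete follow-up must reach 8/150 = 5.3%, 12/200 = 6.0% or 16/250 = 6.4% before any imputation can tip it. With 5 observed complications these become 3/150 = 2.0%, 7/200 = 3.5% and 11/250 = 4.4%. A Kaplan-Meier log-log limit also fails at 8, 12 and 16; a plain limit fails at 10, 14 and 18. Much of the gap between the two rules arises because one adds subjects to the denominator and the other reassigns subjects already in it.

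**The case against.** The strongest reply is on safety. The plan openly sets the scope to enrolled subjects, and its second aim, the effect of missing data on the results, can accommodate an all-enrolled stress test. That stands: the analysis is a disclosed choice and can be kept, provided it is labelled for what it is.

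A reader might infer that the plan ignores scanned subjects lost before MRI + 1 Month and so never tests the censoring assumption behind Kaplan-Meier. The documents do not support that. The visible text does not name those subjects as missing, but the redacted block in Section 13.1.1.3 may hold censoring rules.

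The size of the never-scanned group is also unknown. Section 13.1 is headed Phase I only. Under Section 11.1.1, subjects from earlier protocol versions who decline the study scan roll into Phase II unless they withdraw. Under Sections 11.3.2 and 12.3, subjects meeting exclusion 3 or 5 after consent are consent ineligible and not counted as enrolled. The assumed 10% to 30% has no source in the documents.

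Finally, the visible text attaches no decision rule to any tipping point. That limits the consequence but does not remove the sensed-amplitude inconsistency, which rests on no redacted text.

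**Conclusion.** The sensed-amplitude rule is wrong as written. It imputes outcomes for subjects whom the endpoint definition excludes, so the reported tipping point is not a measure of sensitivity to missing data. The size depends on assumed counts. In the cases worked, the change ranges from 5 of 25 against 3 of 5 to a tipping point of 17 of 24 that disappears altogether, and the direction is not fixed.

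The safety point is secondary and conditional. Scan-related complications are imputed to subjects outside the scanned population, but whether scanned subjects with incomplete follow-up are handled elsewhere cannot be settled from the visible text.

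A reader might also infer that a primary test is biased or its error rate inflated. It is not: the primary analyses exclude these subjects correctly, and only the sensitivity analyses change. This is a minor correction.

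**What to change.** In Sections 13.1.3.3 and 13.1.5.3, state that subjects with a pre-scan average below 5 mV are left out of the tipping-point sets. Keep subjects without paired measurements and the other four listed exclusions as missing. Report the number below 5 mV separately.

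In Section 13.1.1.3, unless the redacted text already does so, add a tipping-point analysis on subjects whose study scan was initiated but whose follow-up to MRI + 1 Month is incomplete. Label the all-enrolled imputation as supplementary, state that it refers to Phase I, and report never-scanned subjects by reason.

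The cost is wording only, with no new data or visits. Section 13.5.5 already provides for an amended SAP approved before the analyses are performed. The sponsor should accept that the tipping points may look better or worse than under the current rules.
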